3.6. Removal of Subjects from Therapy or Assessment

In accordance with the Declaration of Helsinki, subjects will be free to withdraw from the study at any time if they wish so, for any reason specified or unspecified.

The following reasons will be accepted for study discontinuation:

- Withdrawal of subject consent, or loss to follow-up, or inability to remain under medical observation including post study examination,
- Non-compliance or major deviation from the protocol,
- Appearance of a serious AE (SAE),
- New significant information (French regulation : “fait nouveau”), any new fact concerning the research or the study product which may jeopardize the participants’ safety, and which leads the Sponsor or Investigator to take appropriate urgent security decision,
- Any other situation where, in the opinion of the Investigator, continuation of the study would not be in the interest of the subject,
- Discontinuation of the study by the Sponsor.

Should any of the subjects be withdrawn from the study, the Sponsor’s representative and Investigator will discuss the possibility of replacement. All subjects withdrawing for reasons unrelated to the investigational product will have to be replaced. The reason for withdrawal will have to be recorded in the e-CRF for all withdrawn subjects.

The e-CRF has to be completed up to the time of drop out. All drop outs after the first intake of investigational product should be given a post-study assessment as appropriate. The premature termination form in the e-CRF must be completed for all drop outs.

All data, including any drug concentrations from any withdrawn subject, has to be included in the final report. These data will only be evaluated if both the Sponsor and the Investigator agree that it is valid to do so.

Subjects withdrawn because of adverse experiences will undergo a physical examination and laboratory tests planned at the follow-up visit. A follow-up of AEs will also be undertaken for withdrawn subjects.

3.7. Blind and procedures for unblinding

This study is a double blind study.

Randomization will be performed at D1.

3.7.1. Coding list

The analytical centre as well as the Investigator and the team and the subjects will be in blind conditions.

For each subject, randomization envelopes, containing the identification of the treatment (emergency envelopes) will be supplied by Eurofins Optimed and kept in a safe place on site during the whole clinical study period.

In the case of a pharmaceutical preparation is required, the decoding system used is a sealed coding list to be given to the EUROFINS-OPTIMED pharmacist. The sealed coding list should be kept in a safe place and accessible to any person authorised to unblind.

The investigator, CRO staff (except the Pharmacist and pharmacy assistant in charge of the IP final packaging) and Sponsor's clinical trial team members will not have access to the randomization (treatment/product) code except under certain circumstances.

3.7.2. Breaking the blind

The code for any study participant should only be broken by the Investigator or authorised person if it is absolutely necessary.

In case of emergency, for a subject in particular, the code may be broken to ascertain the type of treatment given to study participant concerned. If so, the Investigator (or a person designated from his team) must write his name, signature, date, the number of the participant concerned, the reason for code breaking and the Sponsor must be notified within 24 hours and a full written explanation must be provided.

The code may also be broken by the Clinical Quality Assurance (CQA) representative if this information has to be provided to the physician in charge of subjects treatments (i.e. at the hospital). In this case, the code will be broken using the sealed coding list if available or sealed envelope. The information resulting from code-breaking (i.e., the subject's group assignment) will not be communicated to either the Investigator or the Sponsor.

A copy of the emergency envelopes will be supplied also to the Sponsor. While the Investigator (PI) will operate under blind conditions until the end of the study, the Sponsor may open the code for a single cohort, but only after the study cohort has been completed and the joint (together with the PI) blinded decision, about whether or not to continue with the planned dose escalation, has been taken. The randomization envelopes should not be opened by the Investigator at the end of the study.

In case of Suspected Unexpected Serious Adverse Reaction (SUSAR), the Sponsor Drug Safety should break treatment codes before reporting on an expedited basis the SUSAR to the Competent Authorities and to the Ethics Committee concerned. The blinding code should be broken only for the subject concerned with that SUSAR and treatment code shall not be disclosed to Investigator staff and to Sponsor Clinical Department. An additional copy of the Individual envelopes identified with the subject assignment number is stored by Dompé Drug Safety. Dompé Drug Safety will unmask a patient treatment only for safety reason or to assess regulatory reportability of a potential SUSAR and will document envelope opening.

4. STUDY POPULATION

4.1. Subject inclusion criteria

For eligibility into the trial, subjects must meet all the following inclusion criteria :

- 1- Healthy male subject, aged between 18 and 55 years inclusive;

- 2- Healthy female subject infertile or in post menopause for at least two years, aged between 18 and 60 years inclusive;
- 3- Body Mass Index (BMI) between 18.5 and 29.9 kg/m² inclusive and weight \leq 90kg;
- 4- Considered as healthy after a comprehensive clinical assessment (detailed medical history and complete physical examination);
- 5- Normal Blood Pressure (BP) and Heart Rate (HR) at the screening visit after 10 minutes in supine position:
 - o 90 mmHg \leq Systolic Blood Pressure (SBP) \leq 140 mmHg or 150mmHg for subject > 45 years,
 - o 50 mmHg \leq Diastolic Blood Pressure (DBP) \leq 90 mmHg,
 - o 40 bpm \leq HR \leq 100 bpm,
Or considered NCs by investigators;
- 6- Smoker < 5cigarettes per day who stop totally during the study
- 7- Normal ECG recording on a 12-lead ECG at the screening visit:
 - o 120 \leq PR $<$ 210 ms,
 - o QRS $<$ 120 ms,
 - o QTcf \leq 430 ms for male and \leq 450 ms for female,
 - o No sign of any trouble of sinusual automatism,
Or considered NCs by investigators;
- 8- Normal oral temperature
 - o 36.3°C \leq oral body temperature $<$ 37.5°C;
- 9- Laboratory parameters within the normal range of the laboratory (haematological, blood chemistry tests, urinalysis). Individual values out of the normal range can be accepted if judged clinically non relevant by the Investigator;
- 10- Normal dietary habits;
- 11- Able to communicate well with the Investigator, understand and comply with the requirements of the study, and understand and sign a written informed consent prior to selection;
- 12- Covered by Health Insurance System and / or in compliance with the recommendations of National Law in force relating to biomedical research.

4.2. Subject non-inclusion criteria

Subjects meeting any of the following criteria will not be included into the trial :

- 1- Subject has had a clinically significant illness in the six weeks before screening in the opinion of the Investigator;
- 2- Subject has had a serious adverse reaction or significant hypersensitivity to any drug, has a known clinically significant allergy to anti-inflammatory drugs or chemically related compounds or has a clinically significant allergy to drugs, foods or other materials (in the opinion of the Investigator). However, subjects with mild hayfever may be included in the study.
- 3- Subject has used prescription medication in the 14 days prior to dosing or over-the-counter preparations for 7 days prior to dosing (including vitamin supplements and herbal remedies), with the exception of paracetamol which will be allowed during the study (maximum 500 mg per administration, total daily dose maximum 2 grams).
- 4- Subject has a significant history of drug/solvent abuse or a positive drugs of abuse (DOA) test at any time during the study.
- 5- Subject has a history of alcohol abuse in the last 5 years or currently drinks in excess of 21 and 14 units per week for males and female, respectively, or has a positive alcohol breath test (ABT) at any time during the study.
- 6- Subject is not willing to refrain from caffeine/xanthine containing products in the 48 hours prior to admission to the clinical unit on Day -1 and for the duration of the residential period.
- 7- Subject who has a positive human immunodeficiency virus (HIV) screen, Hepatitis B screen or Hepatitis C screen.
- 8- Subject has donated blood or blood products (e.g., plasma or platelets) within the three months prior to screening.

- 9- Subject who is not suitable to participate in the study in the opinion of the Investigator;
- 10- Subject who has participated in any clinical study with an investigational drug/device within three months prior to the first day of dosing.
- 11- Subject who is in the exclusion period from another study.
- 12- Administrative or legal supervision;
- 13- Subject who would receive more than 4500 euros as indemnities for his participation in biomedical research within the 12 last months, including the indemnities for the present study.

4.3. Subject Identification

4.3.1. Screening number

The screening number will be S and 3 digits, for example: S003. It will be a chronological number. The screening number will be used throughout the screening period, until subjects are randomized.

4.3.2. Inclusion number

The inclusion number will be composed of 7 digits, 3 for the number of centre (001) and 4 for the inclusion number: from 1001 to 1032 for part A and from 2001 to 2036 for part B. It will be a chronological number.

4.3.3. Randomization number

The randomization number will be the same as the inclusion number and the treatment number.

4.4. Subject withdrawal criteria

4.4.1. Definitive or temporary stop of a person's participation in the research

4.4.1.1. List of withdrawal criteria

The criteria of withdrawal could be serious adverse events (SAE) or AEs

4.4.1.2. Reasons for withdrawal

The subjects may withdraw from the study for the following reasons:

- the subject withdraws consent at any time and irrespective of the reason.
- the subject incurs a significant protocol violation that puts the safety of the subject or the integrity of the data at risk (the definition of significant is made contemporaneously by the Investigator).
- at the Investigator's request (for example if the Investigator considers that the subject's health is compromised by remaining in the study or the subject is not sufficiently cooperative).
- at the request of the Sponsor.

4.4.2. Definitive or temporary stop of a part or the totality of the research

4.4.2.1. Decided by the Sponsor

The Sponsor may decide premature discontinuation of the study in the following cases:

- The study is not conducted in accordance with the procedures defined in the approved protocol (i.e. low rate of recruiting - protocol deviations - failure to ensure the quality of the data collected);
- Information on the Investigational Medicinal Product (IMP)/Study Product that might change the current benefit-risk profile of the IMP or that would be sufficient to require changes in the IMP administration or in the overall conduct of the trial;

- Left at the discretion of the Sponsor.

4.4.2.2. Decided by the Investigator

The Investigator may suspend or stop the research if in his judgment the participating subjects are exposed to risks that are not ethically or scientifically justifiable and must notify in writing the Sponsor of this decision providing the reason thereof.

If the research is suspended for safety reasons, the Health Authorities must be immediately notified of the suspension. In this case, the study can resume after an amendment is approved by the Health Authorities.

If the study is stopped, Ethics Committee and Health Authorities should be informed by Sponsor, within 15 days after the decision is taken.

4.5. Premature discontinuation of subject

4.5.1. Data to be collected, and time of recording of these data

Each participant is free to discontinue from the study at any time, for any reason. If a participant discontinues from the study (regardless of the reason for a participant's discontinuation and regardless of the participant's status as evaluable or not evaluable), the Investigator will indicate the reason for discontinuation on the appropriate eCRF page. A follow-up visit will be planned by the Investigator. The exams scheduled for the end-of-study visit will be performed.

In case of premature discontinuation due to AEs, the Investigator will indicate that on the AE Form of the eCRF and in the SAE Form, if appropriate. Participants will be monitored until resolution.

4.5.2. Methods of replacement

A subject who prematurely ends his/her study period after the start of the baseline period and who received treatment will be replaced.

The replacement subject will undergo the complete study. He/she will be given a number corresponding to the number of the subject being replaced plus 100 (i.e. for the subject number 1004, the replacement subject will receive the number 1104).

Subjects who have been withdrawn from the study cannot be re-included in the study. Their inclusion and treatment number must not be re-used.

4.5.3. Methods of follow-up of premature discontinuations

In case of premature discontinuation due to AEs/SAEs, follow-up will continue until the event is resolved or the condition is unlikely to change or the subject is lost to follow-up (see section 8.5).

4.6. Exclusion period

The subjects included in this study will be prohibited from participating simultaneously in other research.

The exclusion period planned at the end of the research will be 3 months.

5. STUDY PRODUCT/TREATMENT

5.1. Description of the treatment(s)

5.1.1. Pharmaceutical form

Name of the compound:	DF 2755A
Pharmaceutical form:	Capsules of 50 mg and 200 mg
Dose per administration:	Part A : 50 mg oad, 150 mg oad, 450 mg oad or 700 mg oad Part B : 100 mg bid, 200 mg bid or 300 mg bid
Number of capsules / administration:	1, 2, 3 or 6 capsules per administration according to the dose level
Timing for administration:	Part A : Single oral dose administration on D1 according to the randomization. The administration will take place at around 8:00 a.m with 200 ml of tap water, in sitting position, in fasting conditions. Part B : Repeated oral administration from Day 1 to Day 14. The administration will take place at around 8:00 a.m and at around 8:00 p.m with 200 ml of tap water, in sitting position, in fasting conditions.
Name of the compound:	Placebo
Pharmaceutical formulation:	Matching capsule of 50mg and 200mg
Dose per administration:	NA
Number of tablets/capsules / administration:	1, 2, 3 or 6 capsules per administration according to the dose level
Timing for administration:	Part A : Single oral dose administration on D1 according to the randomization. The administration will take place at around 8:00 a.m with 200 ml of tap water, in sitting position, in fasting conditions. Part B : Repeated oral administration from Day 1 to Day 14. The administration will take place at around 8:00 a.m and at around 8:00 p.m with 200 ml of tap water, in sitting position, in fasting conditions.

5.1.2. Unit form, manufacture, packaging and labelling

The manufacture of bulk DF2755A capsules and bulk matching placebo capsules and the packaging is carried out, in accordance with Good Manufacturing Practice at:

SYNERLAB DEVELOPPEMENT
 [name]
 [name]

SYNERLAB DEVELOPPEMENT is a sub-contractor of EUROFINS OPTIMED.

IMP (DF2755A and matching placebo capsules) will be shipped to the EUROFINS OPTIMED Pharmacy.

Labelling storage and dispensation of DF2755A capsules and matching placebo capsules, are conducted in accordance with the applicable Good Clinical Practices at EUROFINS OPTIMED Pharmacy

OPTIMED EUROFINS
[name]
[name]

The API is manufactured by AMSA on behalf of Dompé Farmaceutici S.p.A.

AMSA
[name]
[name]

A tripartite quality agreement between Dompé Farmaceutici (the contract giver),EUROFINS OPTIMED and SYNERLAB DEVELOPPEMENT (both contract acceptor) will be in place for the GMP management of any IMP manufacturing activities.

DF2755A and matching placebo capsules will be packaged into blister of 10 capsules. Depending of the doses, capsules will be places in envelope, each envelope containing: Part A: 1, 3, 3 or 6 capsules of DF2755A or matching Placebo; Part B: 2, 1 or 2 capsules of DF2755A or matching Placebo.

Label for blister:

- **DF2755A**

BPS0115 / OP099516.DOM EudraCT N° 2016-003629-41	
Promoteur: DOMPE FARMACEUTICI S.P.A [name] Tel.: [name]	
Investigateur: [name] [name] Eurofins Optimed Clinical Research [name]	
Traitemet: DF2755A – gélules de XX mg 1 blister de 10 gélules	
Lot n° : XXXXXXXXXX Date de péremption : MM/YYYY	
Pour administration orale A utiliser conformément aux indications du protocole A conserver à une température ne dépassant pas 30 °C Pour recherche sur la personne humaine uniquement	

- **PLACEBO**

BPS0115 / OP099516.DOM EudraCT N° 2016-003629-41	
Promoteur: DOMPE FARMACEUTICI S.P.A [name] Tel.: [name]	
Investigateur: [name] [name] Eurofins Optimed Clinical Research [name]	
Traitemet: DF2755A PLACEBO – gélules de XX mg 1 blister de 10 gélules	
Lot n° : XXXXXXXXXX Date de péremption : MM/YYYY	
Pour administration orale A utiliser conformément aux indications du protocole A conserver à une température ne dépassant pas 30 °C Pour recherche sur la personne humaine uniquement	

Labelling operations performed by the EUROFINS OPTIMED Pharmacist, will be in compliance with EudraLex - Volume 4, EU Guidelines to Good Manufacturing Practice Medicinal Products for Human and Veterinary Use - Annex 13.

Labels for unitary doses will bear the following information's:

BPS0115/OP099516.DOM
Dompé farmaceutici s.p.a
[name]
Traitement : DF2755A ou placebo
N° du sujet : 001-XXX
Dose : XXmg soit X gélules
Voie d'administration : orale
A utiliser conformément aux indications du protocole
n°: PREP201
Date de péremption : _ / _ / _
Administration de DXTX : _ / _ / _
Conserver à une température ne dépassant pas 30°C
Pour recherche sur la personne humaine uniquement

The address and telephone number of the main contact for information on the product, clinical trial and for emergency contact will be displayed on study cards that subjects will have been instructed to keep in their possession at all times.

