Investigational Treatment:	
Name of the compound: DF2755A Pharmaceutical form: Capsules of 50 mg, and 200 mg Dose per administration: Part A: 50 mg oad, 150 mg oad, 450 mg oad or 700 mg oad Part B: 100 mg bid, 200 mg bid or 300 mg bid Timing for administration: Part A: Single oral dose administration on D1 according to the randomization. The administration will take place at around 8:00 a.m with 200 ml of tap water, in sitting position, in fasting conditions. Part B: Repeated oral administration from Day 1 to Day 14. The administration will take place at around 8:00 a.m and at around 8:00 p.m with 200 ml of tap water, in sitting position, in fasting conditions.
 
Name of the compound: Placebo Pharmaceutical form: Matching capsule Dose per administration: NA Timing for administration: Part A: Single oral dose administration on D1 according to the randomization. The administration will take place at around 8:00 a.m with 200 ml of tap water, in sitting position, in fasting conditions. Part B: Repeated oral administration from Day 1 to Day 14. The administration will take place at around 8:00 a.m and at around 8:00 p.m with 200 ml of tap water, in sitting position, in fasting conditions.

Subjects:	
Part A: Eight healthy male and female subjects (6 active and 2 placebo) will be included in the four dose level. At least two healthy female subjects will be included in each cohort. One of them should be allocated to placebo. In total, 32 subjects will be enrolled.
 
Part B: Twelve healthy male and female subjects (9 active and 3 placebo) will be included in each dose level. Between three and six healthy female subjects will be included in the cohort. At least one of them should be allocated to placebo. In total, 36 subjects will be enrolled.

Main Evaluation Criteria:	
Primary evaluation criteria: AE, vital signs, 12-lead ECG, laboratory exams.
 
Secondary evaluation criteria: Measurement of pharmacokinetics parameters: C_{max}, t_{max}, λ_z, $t_{1/2}$, AUC_{0-last}, AUC_{inf}, V_z/F, CL/F, Ae_{0-last}, CL_R, total amount in faeces, parent:metabolite(s) ratio. Measurement of Cytokine Inflammation Markers (part B only) and Leukocyte markers (CD11b & CD18), part A except for first cohort and part B.

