3.2. Design

The study is a phase I, single center, double-blind, placebo controlled, randomized, ascending single and repeated doses study in healthy male and female volunteers.

The design consists of a double blind comparison of the test compound versus placebo in which the dose is increased in successive treatment periods.

The Multiple Ascending Dose (MAD) has to be started only after the end of all the cohorts of Single Ascending Dose (SAD). Besides in order to decide to move forward from SAD to MAD, the pharmacokinetic data for all doses administered during SAD will be evaluated (i.e. plasma: quantitative determination of DF2755A bound and unbound; qualitative and preliminary quantitative determination of known metabolites; urine and faeces: qualitative and quantitative determination of parent compound and qualitative and preliminary quantitative investigation of known metabolites).

Dose will be escalated in order to achieve enough safety information on an interval of doses possibly encompassing both the effective dose and the maximum tolerated dose (defined as the highest t dose devoid of any clinical signs/symptoms).

Part A: Single doses of 50 mg oad, 150 mg oad, 450 mg oad or 700 mg oad of DF2755A are planned to be tested in healthy volunteers.

[figure not shown]
Part B: Repeated doses of 100 mg bid, 200 mg bid or 300 mg bid of DF2755A are planned to be tested in healthy volunteers.

The study plan is shown in Figure 7 and 8.

Study procedures are detailed in Section 6 and 7.

Figure 7 - Study plan - Part A

D-21	D-2	D-1	D1	D2	D3	D4
	→					→
	Selection					
Ambulatory Visit		Arrival to the center	Treatment Administration	Hospitalisation	Departure from the center	

Figure 8 - Study plan - Part B

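### The capsule counts in Section 5.1.2 for the top dose of each part (6 for 700 mg, 2 for 300 mg) cannot be made from 50 mg and 200 mg capsules

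*Protocol*

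**What the plan says.** The synopsis, protocol Section 5.1.1 and SAP Section 2.5 name two strengths of active drug and no others ("Capsules of 50 mg and 200 mg"). The placebo row of Section 5.1.1 matches them ("Matching capsule of 50mg and 200mg").

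Section 3.2 plans these doses:

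- Part A: "Single doses of 50 mg oad, 150 mg oad, 450 mg oad or 700 mg oad of DF2755A"
- Part B: "Repeated doses of 100 mg bid, 200 mg bid or 300 mg bid of DF2755A"

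Capsule counts appear in two places. Section 5.1.1 gives, for both active and placebo, "1, 2, 3 or 6 capsules per administration according to the dose level". Section 5.1.2 says that envelope contents depend on the dose and lists them as "Part A: 1, 3, 3 or 6 capsules of DF2755A or matching Placebo; Part B: 2, 1 or 2 capsules". The unit-dose label template in the same section has a line for the dose in mg followed by the number of capsules it corresponds to.

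**The concern.** The list in Section 5.1.2 has four counts for the four Part A doses and three for the three Part B doses, so it reads as one count per dose level in ascending order. With only two strengths, a given number of capsules can reach only a few totals. At the highest dose of each part the planned dose is not among them.

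If that is right, the packaging instruction and the mg dose cannot both be followed at those levels, and a label carrying both figures would contradict itself. These are also the levels with the smallest safety margins in their parts in Section 1.4: 1.67 at 700 mg and 1.94 at 300 mg bid. The dosing instruction should leave no doubt there.

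**Working it through.** **Inputs.** Strengths of 50 mg and 200 mg (synopsis; Section 5.1.1; SAP Section 2.5). Doses of 50, 150, 450 and 700 mg, and of 100, 200 and 300 mg per intake (Sections 3.2 and 5.1.1). Counts of 1, 3, 3, 6 and 2, 1, 2 (Section 5.1.2), and of 1, 2, 3 or 6 (Section 5.1.1).

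**Formula.** If *n* capsules include *b* of 200 mg and *n* − *b* of 50 mg, the total is 50(*n* − *b*) + 200*b* = 50*n* + 150*b* mg. A dose *D* can be made with *n* capsules only if *b* = (*D* − 50*n*)/150 is a whole number from 0 to *n*.

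**Section 5.1.2, in dose order**

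| Part | Dose (mg) | Stated *n* | *b* = (*D* − 50*n*)/150 | Result | All counts that work |
|---|---|---|---|---|---|
| A | 50 | 1 | 0/150 = 0 | 1×50, fits | 1 |
| A | 150 | 3 | 0/150 = 0 | 3×50, fits | 3 |
| A | 450 | 3 | 300/150 = 2 | 2×200 + 1×50, fits | 3, 6, 9 |
| A | 700 | 6 | 400/150 = 2.67 | **impossible** | 5, 8, 11, 14 |
| B | 100 | 2 | 0/150 = 0 | 2×50, fits | 2 |
| B | 200 | 1 | 150/150 = 1 | 1×200, fits | 1, 4 |
| B | 300 | 2 | 200/150 = 1.33 | **impossible** | 3, 6 |

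Six capsules can total 300, 450, 600, 750, 900, 1050 or 1200 mg. Two can total 100, 250 or 400 mg.

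**Section 5.1.1.** For 700 mg, *n* = 1, 2, 3 and 6 give *b* = 4.33, 4, 3.67 and 2.67. The only whole number is 4, at *n* = 2, and two capsules cannot include four of 200 mg. So no listed count makes 700 mg. For 300 mg, *n* = 3 gives *b* = 1 (1×200 + 2×50) and *n* = 6 gives *b* = 0 (6×50). Both work, and both contradict the 2 in Section 5.1.2.

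**Other readings**

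- *Reordering within a part.* 700 mg needs 5, 8, 11 or 14, and none of these is in the Part A list. 300 mg needs 3 or 6, and neither is in the Part B list.
- *A Part B envelope holding the day's 600 mg.* Two capsules reach at most 400 mg.
- *Placebo filler.* Five active capsules plus one placebo would make 700 mg from six, but no filler is described. A filler cannot make 300 mg from two capsules.
- *Several envelopes of the same count.* Envelopes of 6 give 6, 12 or 18 capsules, and none of these makes 700 mg. Three envelopes of 2×50 mg would make 300 mg, but no section describes this.

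**Distance from the planned dose, for illustration.** With six capsules the nearest totals either side of 700 mg are 600 mg (600/700 − 1 = −14.3%) and 750 mg (750/700 − 1 = +7.1%). With two capsules the nearest totals either side of 300 mg are 250 mg (250/300 − 1 = −16.7%) and 400 mg (400/300 − 1 = +33.3%). These are neither bounds nor predicted dosing errors.

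**The case against.** The arithmetic is not in dispute. The strongest case against concerns the reading and the weight.

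Section 5.1.2 does not pair counts with doses explicitly, and envelopes of different counts could be combined. For example, 2×50 mg plus 1×200 mg makes 300 mg, and 3×200 mg plus two single 50 mg capsules makes 700 mg, all with envelope counts listed for the same part. That is possible on paper. However, it borrows counts that fit other dose levels, no section describes it, it leaves the 6 unexplained, and the unit-dose label ties one dose to one count. Five exact matches out of seven in dose order also make the pairing hard to doubt.

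The two levels are not equally affected, and that point stands. At 700 mg both sections fail. At 300 mg only the packaging paragraph fails, since Section 5.1.1 lists workable counts.

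The limits on consequence also stand:

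- Part B doses may change after Part A (Section 1.4).
- The SAP describes Part A randomization in the past tense (Sections 2.1 and 2.3), so the 700 mg cohort may already have been dosed.
- A sponsor-approved pharmacy manual governs preparation and dispensing (Section 5.2.2).
- Dosing is supervised (Section 5.1.3).
- The dose received is recorded and listed (protocol Section 10.1.1.4; SAP Section 5).
- No planned analysis uses the capsule count.

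These safeguards reduce the risk but do not make the counts correct.

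**Conclusion.** The concern holds. Two of the seven counts in Section 5.1.2 are impossible with the stated strengths, and at 700 mg the counts in Section 5.1.1 fail as well. The conclusion assumes that one envelope serves one administration, that the counts follow dose order, and that only active capsules count towards an active dose. The reordered, whole-day and equal-count readings do not repair 700 mg. At 300 mg only an arrangement that the protocol does not describe would work.

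Severity is minor. This is a definite error in a packaging and dosing instruction at the top dose of each part, with small practical risk and no sign that a wrong dose was or would be given. The pharmacy manual was not available, so whether it already carries correct counts is unknown.

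**What to change.** In Sections 5.1.1 and 5.1.2, give the number of 50 mg and 200 mg capsules for each dose level, identical for active and placebo. The documents do not fix the strength mix, so the sponsor must choose it. With the fewest capsules it would be:

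| Dose (mg) | 200 mg capsules | 50 mg capsules | Count |
|---|---|---|---|
| 50 | 0 | 1 | 1 |
| 150 | 0 | 3 | 3 |
| 450 | 2 | 1 | 3 |
| 700 | 3 | 2 | 5 |
| 100 | 0 | 2 | 2 |
| 200 | 1 | 0 | 1 |
| 300 | 1 | 2 | 3 |

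Section 5.1.2 would then read 1, 3, 3 or 5 for Part A and 2, 1 or 3 for Part B. Both rows of Section 5.1.1 would read 1, 2, 3 or 5.

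Check the pharmacy manual and unit-dose labels against the chosen counts. If the 700 mg cohort has been dosed, compare the quantities on the accountability form (Section 5.2.2) with the administered dose in mg (SAP Section 5). Correct Part B in the substantial amendment already required before it starts (Sections 1.4 and 12.3).

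The cost is a few numbers and a document check, with no extra subjects or procedures.
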